## For Ketones greater than ( $>$ ) 1.5 mmol/L and less than ( $<$ ) 3 mmol/L

- In-clinic procedures may continue
- Administer oral hydration with sugar free, caffeine free liquids (if subject is able to drink) or IV fluid hydration (if needed):
  - 22 years and older: 100 cc/hour of 0.9 NS for 2 hours
  - 2-21 years rate for IV fluid hydration is 10 cc/kg given over 2 hours.
- The maximum amount of saline to be infused per kg during the YSI™\* FST is:
  - 60 ml/kg, however it is preferred to have no more than 50 ml/kg for (7 – 80 years).
  - 20 ml/kg for (2 – 6 years).
- Insulin should be administered for ketones with blood glucose greater than or equal to ( $\geq$ ) 250 mg/dL
- For subjects treated with CSII, the catheter should be changed and the correction dose of insulin should be administered subcutaneously.
- If ketones do not decrease to less than or equal to ( $\leq$ ) 1.5 mmol/L after 2 hours of hydration, the study should be stopped
- The study should be stopped if the subject develops nausea, vomiting, or abdominal pain.
- If subject shows signs of fluid overload (i.e., CHF, lower extremity edema, crackles on lung auscultation of S3 heart sound) then rate of IV hydration will be decreased to half the current rate

b) Ketone level greater than or equal ( $\geq$ ) to 3 mmol/L and with no symptoms of ketoacidosis (nausea, vomiting, or abdominal pain) regardless of glucose level.

- The in-clinic procedures will be stopped
- Subjects will be instructed to replace their current infusion set with new infusion set and give subcutaneous dose of correction insulin with syringe or pen if needed. Patients on insulin injections should give correction insulin.
- Administer oral hydration with sugar free, caffeine free liquids (if subject is able to drink) or IV fluid hydration (if needed):
  - 22 years and older: 100 cc/hour of 0.9 NS for 2 hours
  - 2-21 years rate for IV fluid hydration is 10 cc/kg given over 2 hours.
- The maximum amount of saline to be infused per kg during the YSI™\* FST is:
  - 60 ml/kg, however it is preferred to have no more than 50 ml/kg for 7 – 80 years.
  - 20 ml/kg for 2 – 6 years.
- If ketone levels do not return to less than (<) 1.5 mmol/L after 2 hours of oral hydration or IV fluids the subject will be referred to an emergency department and clinic procedures are stopped
- If subject shows signs of fluid overload (i.e., CHF, lower extremity edema, crackles on lung auscultation of S3 heart sound) then rate of IV hydration will be decreased to 50 cc/hour

c) Subject is exhibiting signs and symptoms of DKA. The following guidelines to determine the signs of DKA requiring insulin administration are the following:

- Glucose greater than or equal to ( $\geq$ ) 250 mg/dL
- Ketone levels above 1.5 mmol/L
- With symptoms of nausea, vomiting and/or abdominal pain
- If ketone levels do not return to less than or equal to ( $\leq$ ) 1.5 mmol/L after 2 hours of oral hydration or IV fluids the subject will be referred to an emergency department and clinic procedures are stopped
- Administer oral hydration with sugar free, caffeine free liquids (if subject is able to drink) or IV fluid hydration (if needed):
  - 22 years and older: 100 cc/hour of 0.9 NS for 2 hours
  - 2-21 years: rate for IV fluid hydration is 10 cc/kg given over 2 hours
  - The maximum saline infusion rate is 30 cc/kg for 2-6 year olds

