## Hypoglycemic and Hyperglycemic Challenges

### **Subjects 2 - 13 years:**

During the day of YSI™\*/SMBG FST, subjects (2 - 13 years) will not participate in hypoglycemic and hyperglycemic challenges.

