### **10.5.4. Treatment Guidelines Based on Ketones (Investigator Discretion May Be Used for Medical Management)**

- a) Ketone level greater than or equal to ( $\geq$ ) 0.6 mmol/L and less than ( $<$ ) 3.0 mmol/L with no symptoms of ketoacidosis (nausea, vomiting, or abdominal pain) and for glucose less than or equal to ( $\leq$ ) 500 mg/dL the following should occur:

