## For Ketones greater than or equal to ( $\geq$ ) 0.6 mmol/L and less than or equal to ( $\leq$ 1.5) mmol/L

- In-clinic procedures may continue
- Administer oral hydration with sugar free, caffeine free liquids (if subject is able to drink) or IV fluid hydration (if needed):
  - 22 years and older: 100 cc/hour of 0.9 normal saline (NS) for 2 hours
  - 2-21 years rate for IV fluid hydration is 10 cc/kg given over 2 hours.
- If no nausea, vomiting, or abdominal pain, subjects may continue with hydration for a maximum of 2 hours with glucose greater than ( $>$ ) 250 mg/dL with ketones greater than or equal to ( $\geq$ ) 0.6 mmol/L and less than or equal to ( $\leq$ ) 1.5 mmol/L before insulin is administered
- The maximum amount of saline to be infused per kg during the YSI™\* FST is:
  - 60 ml/kg, however it is preferred to have no more than 50 ml/kg for (7 – 80 years).
  - 20 ml/kg for (2 – 6 years).
- For subjects treated with CSII, the catheter should be changed if glucose is greater than or equal to ( $\geq$ ) 250 mg/dL for 2 hours and insulin should be administered with a syringe
- If subjects develop nausea, vomiting, or abdominal pain, the study should be stopped.
- If subject shows signs of fluid overload (i.e., congestive heart failure (CHF), lower extremity edema, crackles on lung auscultation of S3 heart sound) then rate of IV hydration will be decreased to half the current rate

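### Protocol 10.5.4(b) sets a flat 50 cc/hour on signs of fluid overload, which cuts the ordered weight-based rate by less than half in a child under 20 kg

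*Protocol*

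**What the plan says.** Section 10.5.4 of the Protocol sets IV hydration by ketone tier. Every tier orders the same starting rates, with small differences in wording: "22 years and older: 100 cc/hour of 0.9 NS for 2 hours" and "2-21 years rate for IV fluid hydration is 10 cc/kg given over 2 hours".

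The tiers differ in what they do when signs of fluid overload appear:

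- Part (a), both ketone strata (0.6 to 1.5 mmol/L, and above 1.5 to below 3 mmol/L): "then rate of IV hydration will be decreased to half the current rate".
- Part (b), ketones of 3 mmol/L or more without symptoms: "then rate of IV hydration will be decreased to 50 cc/hour".
- Part (c), suspected DKA: no overload line. Section 11.1 calls for less IV fluid on overload signs but gives no amount.

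For ages 2-6, parts (a) and (b) cap total saline during the FST at 20 ml/kg. The section title qualifies all of this: "Treatment Guidelines Based on Ketones (Investigator Discretion May Be Used for Medical Management".

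**The concern.** The figure in part (b) fits an adult order of 100 cc/hour. The order for ages 2-21 scales with weight, but the reduced rate does not. The lighter the child, the closer the ordered rate already is to 50 cc/hour and the smaller the reduction. The smallest subjects therefore get the weakest written response to fluid overload, in a higher ketone tier than part (a).

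The study enrolls from age 2, with minimums of 15 subjects aged 2-4 and 15 aged 5-6 (Section 7.1). Section 10.5.4 itself gives this age group an IV rate and saline caps. Section 9.2.2.6.2 tests ketones in ages 2-13 on arrival, when glucose exceeds 300 mg/dL, and before discharge. The instruction can therefore be reached in small children. What is at stake is the safety of an individual child, not the trial's inference.

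**Working it through.** **Inputs (all from Section 10.5.4).** Ordered rate from age 22: 100 cc/h. Ordered rate for ages 2-21: 10 cc/kg over 2 h. Rate on overload in (b): 50 cc/h. Rule on overload in (a): half the running rate. Body weight W is assumed, because the documents give none. The infusion is assumed to be running at the ordered rate when overload appears.

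**Reproducing the plan's figure.** Age 22 and older: 100 / 2 = 50 cc/h. The fixed number is exactly the half-rate for the adult order.

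**Ages 2-21.**

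- Ordered rate = 10W / 2 = 5W cc/h.
- Cut under (b) = 1 − 50/(5W) = 1 − 10/W.
- Half the ordered rate = 2.5W cc/h.
- The cut equals 50% when 10/W = 0.5, so at W = 20 kg. It is zero at W = 10 kg.
- Upper bound on extra fluid against halving, if overload appears at the start of a 2-hour order = 2 × (50 − 2.5W) = 100 − 5W mL.

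| Assumed W (kg) | Ordered (cc/h) | Under (b) (cc/h) | Cut under (b) | Half-rate (cc/h) | Extra over 2 h, at most |
|---|---|---|---|---|---|
| 10 | 50 | 50 | 0% | 25 | 50 mL |
| 12 | 60 | 50 | 17% | 30 | 40 mL |
| 15 | 75 | 50 | 33% | 37.5 | 25 mL |
| 18 | 90 | 50 | 44% | 45 | 10 mL |
| 20 | 100 | 50 | 50% | 50 | 0 mL |
| 30 | 150 | 50 | 67% | 75 | none |
| 60 | 300 | 50 | 83% | 150 | none |

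The shortfall is confined to weights below 20 kg. Above 20 kg the fixed rate cuts by more than half, which is not a fault.

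**Candidate replacement rules.** Halving alone would raise the written rate in heavier subjects aged 2-21, to 75 cc/h at 30 kg and 150 cc/h at 60 kg. Taking the lower of 2.5W and 50 gives 25, 30, 37.5, 45, 50, 50 and 50 cc/h at the seven weights in the table. That is a cut of at least 50% everywhere and never more than the present 50 cc/h. From age 22 it gives the lower of 100/2 and 50, which is 50 cc/h and so unchanged.

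**Against the protocol's own cap.** With no reduction at all, one order delivers 10 cc/kg, half of the 20 ml/kg allowed for ages 2-6.

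**The case against.** The case for leaving the text alone has several sound parts.

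- *The standard is borrowed.* Part (b) never promises a 50% cut; halving is part (a)'s rule. A reader might infer that part (b) breaks its own rule or that 50 cc/hour is simply an error. The documents do not support that. What they show is a rate that is not adjusted for weight and gives small children a smaller cut than the neighbouring tier.
- *The extreme case does not fit the wording.* The line calls for a decrease, and at 10 kg there would be none. A clinician would notice, and the section allows discretion. This stands for 10 kg, but not for 12 to 18 kg, where the line can be followed as written and yields a cut below half. Discretion does not correct the figure either. In Section 10.5.5 the protocol says beside the dextrose dose that it may be adjusted for age; the 50 cc/hour line has no such note.
- *The case is rare.* It needs ketones of 3 mmol/L or more without symptoms, IV rather than oral fluid, overload signs and a weight under 20 kg. Section 9.1 states that "subjects (2 - 13 years) will not participate in hypoglycemic and hyperglycemic challenges". Ages 2-6 have fingerstick sessions only. Ages 7-13 do have IV sampling, but that any of them weigh under 20 kg is a further assumption. Exclusion criterion 12 removes anyone with a history of congestive heart failure. All of this stands and sets the severity.
- *Other safeguards exist.* Part (b) has already stopped in-clinic procedures and sends subjects to an emergency department if ketones have not fallen after 2 hours. Section 11.1 sends subjects still overloaded at discharge to the ER. These limit the consequence, but none sets the infusion rate in the meantime.

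A second tempting reading concerns part (c): "The maximum saline infusion rate is 30 cc/kg for 2-6 year olds". It is called a rate but has no time unit. A reader might infer a contradiction with the 20 ml/kg cap. The text does not establish one: a higher limit for the DKA tier may be intended, and a single 10 cc/kg order reaches neither figure. It is a drafting note only.

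**Conclusion.** The point holds as a minor pediatric safety correction. Part (b)'s fixed rate matches part (a)'s halving at age 22 and older and at exactly 20 kg, exceeds it above 20 kg, and falls short only below 20 kg. Within the assumed range of 10 to 20 kg, the shortfall against halving is at most 25 cc/h, or 50 mL over a full 2-hour order.

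The arithmetic is exact. Whether any subject is affected depends on assumed weights and on several uncommon events coinciding. The documents do not support a claim that children would be taken past the protocol's fluid limits, since a single order stays within the 20 ml/kg cap for ages 2-6. No endpoint, alpha or sample size is affected.

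**What to change.** In Section 10.5.4(b), change the overload instruction so that IV hydration is *reduced to half the rate then running or to 50 cc/hour, whichever is lower*. Put the same line in part (c). While the section is open, the sponsor's medical team can state what the 30 cc/kg figure in part (c) means.

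There is no statistical or enrolment cost. The work is a short wording amendment, sent to up to 17 centers. Under Section 17.6, if it is classed as significant it needs IRB approval and, where applicable, regulatory approval before use; investigators sign any approved amendment. If classed as administrative, it goes to the IRB for notification. It could travel with the next planned amendment.

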## 10.5.5. **Rescue Therapy/Low Glucose Guidelines for Subjects "Undergoing Observation Only":**

### **Glucose less than (<) 50 mg/dL**

- Severe hypoglycemia - see definition Section 12.1
- Subject had seizure, loss of consciousness, or altered mental status so uncooperative with food or liquid orally. Subject will be withdrawn from study (stop the challenge, stop the YSI™\*/SMBG FST and DO NOT continue with any future scheduled frequent sampling days).
  - Dextrose: 25 grams of dextrose using an ampule (50 ml/25 grams of dextrose) of Dextrose 50% IV push over 3 minutes. Repeat administration

may be given again after 15 minutes if glucose is not above 100 mg/dL. This dose may be adjusted according to investigator discretion based on subject age and other clinical considerations.

- Glucagon emergency kit (glucagon for injection [ribosomal DNA, rDNA origin] 1 mg, with 1 mL of diluting solution administered intramuscular (IM): only given if Dextrose was not able to be given due to IV access.
- Target glucose 100 mg/dL
- Low Glucose without altered level of consciousness
  - Replacement simple carbohydrate may be administered per investigator discretion to a target of above 75 mg/dL (e.g. 15 grams/every 15 minutes).

## **Glucose 50-75 mg/dL**

- Replacement carbohydrate may be administered per investigator discretion to a target of above 75 mg/dL. (e.g. 15 grams/every 15 minutes).
- Please see the Hypoglycemic and Hyperglycemic Challenge Guidelines for instructions on treating hypoglycemia for the hypoglycemic challenge.
- In this range, insulin should not be given until glucose is at least above 100 mg/dL.

## **10.5.6. Instructions for Guidelines on Approach to Low and High Glucose for Subjects Undergoing Challenge:**

See Hypoglycemic and Hyperglycemic Challenge Guidelines.

If the subject has taken insulin at home, the following guidelines must be followed:

- Subject must wait 3 hours from last bolus dose of home insulin before a challenge is started.
- Subject will only perform one challenge that day, if the insulin bolus at home was within 3 hours from the start of YSI™\* FST.

## **10.5.7. End of Challenges and Discharge**

Please refer to the Discharge Criteria Guidelines.

## **10.5.8. Additional discharge activities**

- Investigational center staff will provide 24-hour contact information to the subjects
- Investigational center will contact the subject within 24 hours after discharge to assess subject status

- Subjects will be requested to continue to monitor their glucose at home with a minimum of 4 fingerstick glucose readings a day and a target of 7 fingersticks a day.

## 10.6. Glucose and Glycemia Measurements

During the course of the study, the subjects' blood glucose, SG levels, HbA1c, blood ketone, and alternate POC blood glucose values will be assessed using the following methods:

- **Daily blood glucose**- Values will be assessed during the study by all subjects using the CONTOUR®NEXT LINK 2.4 study meter. The control solution test will be done following the manufacturer's IFU. Subjects will be trained on the use of the CONTOUR®NEXT LINK 2.4 study meter per the manufacturer's IFU.
- **YSI™\* FST blood glucose values** -During the YSI™\* FSTs at the investigational center, blood plasma glucose will be determined using the laboratory blood glucose analyzer (YSI™\*).
- **Blood ketone values** – During the YSI™\*/SMBG FSTs at the investigational center, blood ketones will be determined by all subjects using the Precision Xtra™\* ketone meter. A QC test will be performed on the meter assigned to each subject before each YSI™\*/SMBG FST. The results of the QC test will be documented in the subject's source documents. The QC test will be done following the manufacturer's IFU. Study staff will be trained on the use of the Precision Xtra™\* ketone meter per the manufacturer's IFU. All ketone measurements will be logged in the subject records, and recorded on the appropriate eCRF.
- **SGVs** - Assessed using the following methods:
  - SGVs collected by subject's Guardian™ Connect Transmitter
- **HbA1c** - Collected at baseline (Visit 1) and will be used as demographic information.
- **Alternate POC blood glucose values**- During the YSI™\*/SMBG FST at the investigational center, alternate POC blood glucose measurements will be used (CONTOUR®NEXT LINK 2.4 study meter) and the values recorded on the appropriate eCRF (not used for analysis). A QC test will be performed on the CONTOUR®NEXT LINK 2.4 study meter device before each YSI™\*/SMBG FST. The results of the QC test will be documented in the subject's source documents. The QC test will be done following the manufacturer's IFU.

## 10.7. Recording Data

All data required for analysis will be captured on eCRFs using OC-RDC's module. Original eCRFs will not be used to capture raw/source data and supporting documentation will be required.

Electronic device data will be collected from the CONTOUR®NEXT LINK 2.4 study meter using Medtronic CareLink™ Personal For Clinical Research software. The system uses Secure Sockets Layers (TLS) technology, which encrypts all data it stores (21 CFR Part 11 compliant). Data from the Guardian™ Connect Transmitter will be collected using the GST Download Utility Software. Certain data points stored

in the uploaded information may also be captured on the appropriate eCRF. These data files will be sent to the sponsor electronically using the internet and a secure cloud-based site (Box).

Electronic data files will be collected from the YSI™\* devices for each subject. These data files will be sent to the sponsor electronically using the internet and a secure cloud-based site (Box).

Laboratory results will be recorded on eCRFs.

The Investigator will ensure that all eCRFs are completed promptly, completely, and accurately. Only authorized study personnel are permitted to enter data and sign eCRFs. These tasks may be delegated by the Investigator as desired and noted on the delegation of authority log. Information on eCRFs must conform to the information in the source documents. Medtronic will provide detailed instructions to assist with eCRF completion. In the event of data discrepancies, investigational centers will be asked to resolve queries electronically in the OC-RDC system; otherwise, irresolvable data-related issues will be routed to the sponsor for review and final disposition. An audit trail is maintained in OC-RDC to capture any corrections or changes of the eCRFs. System backups for data stored in the OC-RDC system will be consistent with Medtronic standard procedures.

Medtronic will only consider eCRFs to be complete when all discrepancies between source data and eCRF have been resolved and eCRF content has been reviewed by a Study Monitor. In addition, specific eCRFs must also be reviewed and electronically signed by the Investigator, indicating his/her agreement with the accuracy of all recorded data. It is expected that the Investigator and his/her staff will cooperate with the monitoring team and provide any missing data in a timely manner.

## 10.8. Deviation Handling

A deviation is any instance(s) of failure to follow, intentionally or unintentionally, the requirements of the CIP. It is expected that the investigator will conduct this clinical trial in compliance with the CIP and all applicable regulations governing the conduct of clinical research involving human subjects. Failure to do so could result in one or all of the following:

- Investigational center disqualification
- Notification to the regulatory authorities/IRB depending on the severity of the deviation and reporting requirements

The investigator should not implement any deviation from, or changes to, the CIP without agreement by the sponsor and prior review and documented approval/favorable opinion from the IRB, except where necessary to eliminate an immediate hazard(s) to trial subjects or when the change does not affect the scientific soundness of the plan or the rights, safety, and welfare of the subjects.

Deviations related to:

Blood glucose range and duration targets:

Blood glucose range and duration targets listed for the hypoglycemic and hyperglycemic challenges are targets. It is expected that the investigational centers participating in the study will make their best efforts to reach these targets with the subjects who participate in these challenges, but the sponsor understands that managing diabetes itself is a challenge and meeting these target values and durations for all subjects may not always be possible.

In the event that samples are not able to be collected or analyzed for technical reasons (YSI™\* or IV line problems) reasons must be recorded on the eCRF and will not be considered deviations.

FST timing:

Out of window protocol deviations related to start of FST time will be given if the patient does not come on the scheduled day of FST only.

FST Sample:

It is noted that collecting YSI™\*/SMBG FST every 5 – 30 minutes may be challenging. Deviations for missing YSI™\*/SMBG FST samples will be issued for the following reasons:

- If there are 2 consecutive YSI™\*/SMBG FST samples missing (unless they were missed for safety issues, IV or YSI™\* FST device issues). Example of 1 missing YSI™\*/SMBG FST:
  - YSI™\*/SMBG FST at 8 A.M. which is 65 mg/dL
  - YSI™\*/SMBG FST at 8:15 A.M. which is 60 mg/dLSince the 1st sample is less than (<) 75 mg/dL, the next draw should be in 5 mins (+ 3 - 8 minutes); but the 2nd sample is at 8:15 AM, so there is at least 1 missing sample which could have occurred at latest 8:08 AM
- If there are 3 or more total YSI™\*/SMBG FST samples missing per subject per YSI™\*/SMBG FST (unless they were missed for safety issues, IV or YSI™\* FST device issues).

SMBG:

As subjects may not follow the fingerstick recommendations perfectly, no study deviation will be given unless site did not train subject on SMBG study procedures.

## 10.8.1. Documenting Requirements for Study Deviations

### 10.8.1.1. Unplanned CIP Deviations

The investigator may encounter the need to deviate from the CIP when necessary to protect the safety, rights or well-being of a subject in an emergency or in unforeseen situations beyond the investigator's control (e.g. subject failure to attend scheduled follow-up visits, inadvertent loss of data due to computer malfunction, inability to perform required procedures due to subject illness).

All deviation from the CIP, regardless of the reason should be documented as soon as possible, after the deviation occurs or is identified. This documentation should include deviation date, description of the deviation, the reason for deviation, and the corrective action.

CIP deviations should be reported as follows:

- a) To the IRB for notification/acknowledgement;
- b) To the sponsor and, if required;
- c) To the regulatory agency

## 10.8.1.2. Minor or Administrative CIP deviations

Minor or administrative deviations are those that do not "affect the scientific soundness of the research plan or the rights, safety, or welfare of human subjects."

Deviations that do not meet the criteria for expedited notification or prior regulatory/IRB approval, may be reported at the time of eCRF completion or separately upon discovery such as during monitoring visits.

If a CIP deviation occurs which meets this definition, the deviation should be reported to the IRB at the time the continuing review application is submitted.

